7.2 Assessment of Participant Adherence with Study Agent(s)/Intervention(s)

Adherence to study medications and out of pocket costs will be assessed at the 3 month follow up visit, including assessing for any potential occurrence of treatment crossover.

If participants do not return for the 3 month study visit, they will be contacted by the study research coordinator by phone, mail and/or email. The participant will be asked to return to the clinic for a follow-up appointment. If the participant is unwilling to return, follow up information will be collected by phone or via an email survey assessing for adherence and study outcomes.

7.3 Precautionary and Prohibited Medications and Procedures

In this trial, participants will be randomized to receive either LMWH or aspirin. Participants in this study may not receive any other full dose medication as prophylaxis for anticoagulation or as treatment for a VTE even, nor may they receive additional dosages of aspirin above 81 mg daily. There are no other prohibitions regarding medications management, and participants will be treated according to the local standard of care. Data on specific concomitant medications will be collected (See Section 6.2.1). Should it be determined that the medication the participant was randomized to is no longer clinically appropriate, the study medication will be stopped, the

The PREVENT CLOT study protocol is the confidential intellectual property of the PREVENT CLOT Principal Investigators, Steering Committee, and the University of Maryland Baltimore and METRC and cannot be used in any form without the expressed permission of the Principal Investigators.

research team will record the reason for medication discontinuation, and the participant will continue to be followed through the 3 month follow up.

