2. BACKGROUND INFORMATION AND SCIENTIFIC RATIONALE

2.1 Background Information

Importance of Blood Clots and Blood Clot Prevention Medicines. Preventing venous thromboembolism (VTE) in the legs or lungs is a major unsolved problem in modern medicine. Each year, in the United States alone, blood clots are estimated to affect 300,000 – 600,000 patients.¹ These events may have important consequences for patients. VTE can include both deep venous thrombosis (DVT) and pulmonary embolism (PE). Even minor blood clots require a minimum of 6 months of medication, often with frequent blood tests, and increased risk of medication-related bleeding. At the most severe end, PEs are thought to account for 60,000–100,000 deaths per year in the United States.²

Patients who sustain trauma are well known to be at an increased risk for blood clots throughout their body, including fatal PE's.³ There are 6 million fractures treated each year in the United States alone and 2.3 million patients are admitted each year after trauma.⁴⁻⁶ Hip and femur fractures specifically are among the most common fractures and are associated with a particularly high risk of blood clots.^{7,8} Current guidelines indicate that most orthopaedic trauma patients should be given medication to reduce the risk of blood clots.^{9,10} Despite the common nature of these injuries and the potential devastating impact that blood clots can have on patients' lives, we currently do not know the best prophylactic regimen for these patients.

The ideal clot prevention medication for orthopaedic trauma patients would prevent death from PE and other consequences of blood clots while also limiting complications from the medication, such as bleeding from surgical wounds and other sources.¹¹ A blood clot resulting in death is obviously a devastating outcome for a patient and their family; however, other complications from clot prevention medications are not insignificant and may require surgery and have a major impact on the lives of patients, including, permanent disability in some cases.^{12,13} Even under ideal conditions the medications used to reduce clots cannot completely eliminate the chance of blood clots and in some instances may lead to death themselves.¹²⁻¹⁴

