5.1.2 Participant Exclusion criteria

1. Did the patient present to the hospital more than 48 hours post injury?
2. Has the patient received more than 2 doses of LMWH or Aspirin for initial prophylaxis?

The PREVENT CLOT study protocol is the confidential intellectual property of the PREVENT CLOT Principal Investigators, Steering Committee, and the University of Maryland Baltimore and METRC and cannot be used in any form without the expressed permission of the Principal Investigators.

3. Is the patient on long term blood thinners (other than low-dose aspirin or platelet inhibitors such as Plavix or Aggrenox)?
4. Did the patient have a VTE within the last 6 months?
5. Is the patient on therapeutic (as opposed to prophylactic) blood thinners for an acute issue at the time of admission?
6. Does the patient have a newly diagnosed indication for therapeutic blood thinners (for example vascular injury) that will require therapeutic anticoagulation for more than one week?
7. Does the patient have an allergy to aspirin, or NSAIDs, or a history of heparin induced thrombocytopenia, or other medical contraindication to blood thinners (e.g. peptic ulceration, gastrointestinal bleeding, etc)?
8. Is the patient on higher dose aspirin (>81 mg once a day or higher) for medical reasons or will be treated with higher dose aspirin?
9. Does the patient have underlying chronic clotting disorders (i.e. Factor V Leiden, hemophilia, Protein C and S deficiency) that require full dose anticoagulation or are a contraindication to VTE chemoprophylaxis?
10. Does the patient have end stage renal disease, or impaired creatinine clearance <30 ml/min at time of randomization?
11. Is the patient pregnant or lactating?
12. Does the patient speak neither English nor Spanish?
13. Is the patient is a prisoner?
14. Is the patient is likely to have severe problems maintaining follow-up?
15. Is the patient, based upon the clinical judgment of the treating clinician, NOT equally suited for treatment with either Aspirin or Lovenox?
16. Should the patient be excluded for other reasons at the discretion of the treating physician?
17. Does the patient have a known COVID-19 diagnosis prior to fracture treatment or within 3 months of the index fracture?

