6.2.1 Medical Record Review

For all enrolled participants, data related to the index hospitalization will be collected. This will include a daily check of the medication administration record to ensure that the patient is receiving the study drug to which he/she was assigned and to document adherence. If treatment is stopped, held or changed the research team member will either identify the reason for change from the chart or by asking the primary team if the reason is not documented. Other data to be collected includes orthopaedic and other injury characteristics, admission labs, and complications, including a fatal bleed, ≥ 2 g/dL drop in hemoglobin, reoperation for hematoma evacuation or surgical site infection, other clinically significant bleeding or infectious complication, VTE, PE, and any imaging studies (and results) conducted for bleeding or VTE concerns. Information on the administration of a limited number of concomitant medications with known potential for bleeding side effects will also be collected, including Plavix, or other platelet inhibitors, aspirin, NSAIDs (e.g. toradol, ibuprofen), and any administration of a full dose of anticoagulation medication, as well as the reason, will be recorded.

Due to the potential affects that COVID-19 has on patients, ie increased risk of clotting, COVID-19 status will be recorded if available via medical record review during the index hospitalization and at follow up. Research team member will record whether the patient is experiencing any symptoms related to COVID-19 or has tested positive. Patients who have tested positive during the index hospitalization will be excluded from the study. Patients who test positive between discharge from the index hospitalization and follow up will remain in the study with data collection of COVID-19 status in the case report form. These data will also be retrospectively collected on all patients who have enrolled into the study since January 2020.

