8.1 Definitions

8.1.1 Adverse event

Any untoward or unfavorable medical occurrence in a human subject, including abnormal sign (e.g., abnormal physical exam or laboratory finding), symptom or disease temporally associated with the subject’s participation in the study, whether or not considered related to the subject’s participation. Several adverse events, or complications, will be collected as primary and secondary outcomes of the study. The most severe of these events include: (1) Death, (2) Fatal bleeding into a critical organ (retroperitoneal, intracranial, intraocular, intraspinal); (3) Significant/massive PE central pulmonary embolism with resulting heart strain (PE); (4) Wound drainage or hematoma requiring reoperation; (5) Wound drainage, bleeding or hematoma that does not require reoperation; (6) Bleeding event that requires intervention (e.g. chest tube, interventional radiology embolization); (7) Surgical Site Infection requiring reoperation; (7/8) Surgical site infection that does not lead to reoperation but requiring antibiotic treatment; (9) Greater than 2 mg/dL drop in hemoglobin within 24 hrs; and (10) GI Bleed. These and other

The PREVENT CLOT study protocol is the confidential intellectual property of the PREVENT CLOT Principal Investigators, Steering Committee, and the University of Maryland Baltimore and METRC and cannot be used in any form without the expressed permission of the Principal Investigators.

complications common in the trauma population will be reviewed in aggregate twice annually by the DSMB to assess for differences between treatment groups. They will be reported to the IRB on an annual basis, unless they meet the criteria for Serious Adverse Event (see below).

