8.2.4. Management of Adverse Events

Adverse Events and Serious Adverse Events will be managed according the medical judgment of the treating physician.

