
 • Admission date/time • Discharge date/time • Discharge outcome (discharged/death) • Admission labs (if tested) 
 ◦ INR ◦ PTT ◦ Platelets ◦ Max serum lactate (first 24 hours) ◦ Creatinine ◦ TEG parameters (if ordered) • Surgical data 
 ◦ Surgery info (ortho/non-ortho surgeries) 
 ▪ Dates ▪ Total number of surgeries ▪ Weight bearing status on discharge ◦ Total number of surgeries (ortho/non-ortho) • Imaging studies (and results) conducted for bleeding or VTE 
 ◦ Angiogram ◦ Ventilation perfusion (VQ) scan ◦ Duplex scan/ultrasound ◦ CT angiogram (CTA) ◦ MRI ◦ Other • Complications 
 ◦ fatal bleed ◦ $\geq 2\text{g/dL}$ drop in hemoglobin ◦ reoperation for hematoma evacuation ◦ other clinical significant bleeding ◦ infectious complication ◦ VTE ◦ PE • Concomitant meds 
 ◦ LMWH ◦ Aspirin ◦ Plavix ◦ platelet inhibitors ◦ NSAIDs 			

The PREVENT CLOT study protocol is the confidential intellectual property of the PREVENT CLOT Principal Investigators, Steering Committee, and the University of Maryland Baltimore and METRC and cannot be used in any form without the expressed permission of the Principal Investigators.

	Baseline	Baseline – 3 months	3 month
Assessment			
○ Anticoagulation medications outside treatment assignment			
CRF06: VTE Prophylaxis (Inpatient)	X		
• Pre & Post Randomization Prophylaxis Use • Treatment Arm: Aspirin Dosage (Dose, Dose Unit, Route, Date/Time of Start/Stop of Administration) • Treatment Arm: LMWH Dosage (Dose, Dose Unit, Route, Date/Time of Start/Stop of Administration) • Reasons prophylaxis held or discontinued (if applicable) • Doses ordered vs doses received or missed & reason missed • Treatment crossover information: number of doses & therapeutic anticoagulation therapy status (date, dose, reason)			
CRF07: Clinical Follow-up			X

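### Protocol section 7.3, read literally, bars other full-dose medication for treating a VTE event and so conflicts with section 8.2.4; probably a drafting error, but wrong as written

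*Combined protocol and SAP*

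**What the plan says.** Section 7.3 of protocol Version 11.0, headed as covering precautionary and prohibited medications, says: "Participants in this study may not receive any other full dose medication as prophylaxis for anticoagulation or as treatment for a VTE even". The same sentence also limits additional aspirin. The wording stands unchanged from Version 1.0. The next sentence reads: "There are no other prohibitions regarding medications management, and participants will be treated according to the local standard of care". The section closes by saying that study drug is stopped when it is no longer clinically appropriate, that the reason is recorded, and that follow-up continues to 3 months.

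Section 8.2.4 says: "Adverse Events and Serious Adverse Events will be managed according the medical judgment of the treating physician". Section 8.1.1 includes among the most severe adverse events "Significant/massive PE central pulmonary embolism with resulting heart strain (PE)".

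Several places deal with recording anticoagulation:

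- Section 6.2.1: "any administration of a full dose of anticoagulation medication, as well as the reason, will be recorded".
- Appendix B, CRF05: anticoagulants given outside the treatment assignment, under concomitant medications.
- Appendix B, CRF06: "therapeutic anticoagulation therapy status (date, dose, reason)", as part of the treatment crossover item.
- Appendix B, CRF07: other treatment given for a PE or VTE event.

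**The concern.** PE and DVT are outcomes of this trial, so a participant with a confirmed clot is a foreseeable case that the treatment rules must handle. The section a site would consult on permitted drugs names treatment of a VTE as a prohibited use of other full-dose medication and gives no exception. A site following that sentence to the letter could not freely use the clinical judgment that 8.2.4 grants.

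What is at stake is first a safety instruction. Treating a PE correctly would, on the literal wording, be a departure from the protocol that section 13.6 asks sites to log as a deviation. Section 8.7 also names non-adherence with the protocol as a possible ground for removing a participant. If the sentence were obeyed, treatment of a potentially fatal event would be restricted, and the primary outcome is all-cause mortality by 90 days.

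**Working it through.** No arithmetic applies, since the point depends on no rate, margin, alpha or sample size. The check reads 7.3 against every place in the available text that deals with VTE treatment, full-dose anticoagulation, rescue medication or adverse event management.

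1. **Is it a prohibition, and does it reach treatment?** Yes to both. The sentence says what participants may not receive. Prophylaxis and treatment are joined by *or*, so treatment is a separate limb. The next sentence speaks of there being no *other* prohibitions, which confirms that the first sentence is one.

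2. **Does the standard-of-care wording in 7.3 lift the ban?** No. It follows the statement that nothing else is prohibited, so its natural scope is whatever the ban does not cover. It does not say that it overrides the ban.

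3. **Does stopping study drug lift it?** No. 7.3 allows study drug to be stopped and keeps the patient in follow-up, but names no replacement treatment. The ban applies to participants in the study, and a patient still in follow-up is one.

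4. **Does section 7.4 on rescue medication lift it?** No. It covers only overdose or sensitivity.

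5. **Is there a contrary operative rule?** Yes. 8.2.4 gives the treating physician the management of adverse events. 8.1.1 lists significant or massive PE by name, and its general definition of an untoward medical occurrence would also take in DVT. One rule grants discretion over treatment and the other removes a class of treatment from it.

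6. **What do the recording provisions show?** 6.2.1, CRF05, CRF06 and CRF07 provide for recording full-dose anticoagulation or PE/VTE treatment, so the authors expected it to occur. The adherence definition (protocol 10.5.2, SAP section 5) points the same way: dosage changes and crossovers count as non-adherence only when the reason is non-medical, alongside patient refusal. By implication, a change made to treat a clot is not non-adherence on that ground. But recording a treatment is not permitting it, and the CRF06 item sits under crossover information on a form about prophylaxis.

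7. **How much depends on the word *other*?** It may mean other than the two study medicines. Therapeutic-dose LMWH would then fall outside the ban, but every other full-dose agent would stay barred for VTE treatment. The conflict with 8.2.4 shrinks and does not disappear.

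8. **Two passages that add less than they seem to.** Section 2.1 says "Even minor blood clots require a minimum of 6 months of medication". That is background about why clots matter to patients. It sets no trial procedure and does not say full-dose. Exclusion 6 in section 5.1.2 concerns a newly diagnosed indication "that will require therapeutic anticoagulation for more than one week". It shows that short therapeutic courses were tolerated, but it is an eligibility rule with vascular injury as its example and does not address a clot arising on trial.

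**The case against.** The strongest reply is that this is editorial. The sentence is visibly unedited, with a truncated word at the key point. 8.2.4 is itself a permission, general but operative, so a physician who anticoagulates a PE is following the protocol. The case report forms have fields for the treatment, and the adherence definition does not penalise medically driven changes. No trauma service would leave a confirmed PE untreated because of one clause.

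Most of this stands. It is why the clause is best read as a drafting error and why the point is rated minor. It also rules out saying that the protocol nowhere permits treatment, because 8.2.4 does so in general terms. The accurate statement is that no passage in the available text specifically exempts VTE treatment from the ban. The consent pages, the attachments and the consortium's manual were not available and might say more.

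What does not stand is the inference that nothing needs changing. A general permission beside a specific prohibition is an unresolved conflict, and a reader of 7.3 alone would not know which rule prevails.

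A reader might also be tempted to put section 2.1 on a par with 8.2.4. The documents do not support that: 2.1 reports clinical background and binds no site.

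**Conclusion.** The point holds as an inconsistency that is wrong as written, at minor severity. Its size is one clause of 7.3. No number of patients and no shift in any result is claimed.

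The effect on estimates depends on what sites do. If they treat a confirmed PE or DVT as clinically needed, which is likely, the data are the same as if the clause did not exist and no estimate changes. If they followed the clause, treatment would be withheld or limited after a potentially fatal event, and both patient safety and 90-day mortality could be affected. It would therefore be too flat to say that no estimate can be affected.

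A reader might infer that participants with clots were, or would have been, left untreated, or that the mortality comparison is biased. The documents do not support either inference. The recording provisions and 8.2.4 indicate that treatment was expected, and nothing in the text shows that any site withheld it.

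The conclusion rests on reading the truncated word as *event* and on the text available for review.

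**What to change.** Reword 7.3 so that it bars only other anticoagulants given as prophylaxis alongside study drug. Add that a confirmed PE or DVT is treated per local standard of care, with study drug stopped as clinically appropriate, the treatment recorded on CRF06 or CRF07, and follow-up continued to 90 days.

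The cost is a one-clause amendment and a notice to sites. CRF06 and CRF07 already have the fields, and neither the sample size nor any analysis changes.

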7.4 Rescue Medications

Any need for rescue medication resulting from a drug overdose or sensitivity will be handled per the standard of care at the treating institution or where the patient seeks care.

8. ASSESSMENT OF SAFETY

The study will monitor and report adverse events to ensure patient safety. Definitions and procedures for reporting adverse events are designed to satisfy 45 CFR Part 46, Subpart A; the “Common Rule”, shared by 17 Departments and Agencies as well as 21 CFR 312, the FDA regulation for adverse events. The Common Rule requires written procedures and policies for ensuring reporting of “unanticipated problems” involving risks to participants to IRBs, appropriate institutional officials, and the Department or Agency Head. The approach to defining and reporting events is based on the 2009 FDA Guidance for Clinical Investigators, Sponsors, and IRBs on adverse event reporting to IRBs
(<http://www.fda.gov/downloads/RegulatoryInformation/Guidances/UCM126572.pdf>)

The medical monitor (MM) is responsible for providing medical guidance and overseeing patient safety for the study. The MM participates in determining the course of action necessary to meet safety goals and objectives. This is achieved through the review of Serious Adverse Event reports; resolving safety issues; and interacting with Principal Investigators. Each participating site is responsible for ensuring that all local IRB requirements for reporting adverse events (both internal and external) are met.

8.1 Definitions

8.1.1 Adverse event

Any untoward or unfavorable medical occurrence in a human subject, including abnormal sign (e.g., abnormal physical exam or laboratory finding), symptom or disease temporally associated with the subject’s participation in the study, whether or not considered related to the subject’s participation. Several adverse events, or complications, will be collected as primary and secondary outcomes of the study. The most severe of these events include: (1) Death, (2) Fatal bleeding into a critical organ (retroperitoneal, intracranial, intraocular, intraspinal); (3) Significant/massive PE central pulmonary embolism with resulting heart strain (PE); (4) Wound drainage or hematoma requiring reoperation; (5) Wound drainage, bleeding or hematoma that does not require reoperation; (6) Bleeding event that requires intervention (e.g. chest tube, interventional radiology embolization); (7) Surgical Site Infection requiring reoperation; (7/8) Surgical site infection that does not lead to reoperation but requiring antibiotic treatment; (9) Greater than 2 mg/dL drop in hemoglobin within 24 hrs; and (10) GI Bleed. These and other

The PREVENT CLOT study protocol is the confidential intellectual property of the PREVENT CLOT Principal Investigators, Steering Committee, and the University of Maryland Baltimore and METRC and cannot be used in any form without the expressed permission of the Principal Investigators.

complications common in the trauma population will be reviewed in aggregate twice annually by the DSMB to assess for differences between treatment groups. They will be reported to the IRB on an annual basis, unless they meet the criteria for Serious Adverse Event (see below).

8.1.2 Unanticipated problem

Any incident, experience, or outcome that meets all of the following criteria:

- (1) is unexpected, in terms of nature, severity, or frequency, given the research procedures that are described in the protocol and informed consent document and the characteristics of the patients eligible for the study.
- (2) is related or possibly related to treatment/procedures under study; possibly related means there is a reasonable possibility that the incident, experience, or outcome may have been caused by the study procedures or treatments.
- (3) suggests that the participation in the study may place subjects or others at a greater risk of harm (including physical, psychological, economic, or social harm) than was previously known or recognized.

Please note that not all adverse events are unanticipated problems and only some unanticipated problems are in fact adverse events. For instance, if a laptop containing study data is stolen, this is an unanticipated problem but it is not an adverse event since it is not an untoward or unfavorable medical occurrence in a human subject

